6.1.1.1. G1T38 Dose Evaluation Criteria

In the first Cohort of 6 patients, a relatively low dose of G1T38 will be administered to allow for a sufficient safety window. This low dose of G1T38 is anticipated to be below the maximum tolerated dose (MTD), even if osimertinib increases the systemic exposure of G1T38 (see Section 4.4.2). However, if ≥ 2 of 6 patients experience a DLT, then the MTD will have been exceeded and a lower G1T38 dose level may be explored. If 1 or fewer patient(s) in the first cohort of 6 experience a DLT, then 3 patients may be enrolled at the next SMC recommended G1T38 dose level.

The G1T38 dose evaluation criteria for Cohorts 2 and beyond are listed below.

- If there is no DLT in a given dose level cohort, then 3 patients may be enrolled at the next SMC recommended G1T38 dose level.
- If there is 1 DLT in a given dose level cohort of 3 patients, an additional 3 patients will be enrolled at this G1T38 dose level. If no additional DLTs are observed (ie, ≤ 1 out of 6 with DLT), escalation may proceed to the next SMC recommended G1T38 dose level.
- If there are \geq 2 DLTs in a given dose level cohort, then the MTD will have been exceeded and a lower G1T38 dose level may be explored as determined by the SMC.

6.1.1.2. Definition of Dose-Limiting Toxicities (Applicable to Cycle 1 Day -16 through Cycle 1 Day 28 in Part 1)

Dose-limiting toxicities are drug-related AEs defined as follows:

- Grade 4 neutropenia
- \geq Grade 3 neutropenic infection/febrile neutropenia
- Grade 4 thrombocytopenia
- ≥ Grade 3 thrombocytopenia with bleeding
- \(\geq \) Grade 3 nonhematologic toxicity (additional criteria for nausea, vomiting, diarrhea, or fatigue: lasting > 5 days with maximal medical management)

• Liver function test abnormalities meeting Hy's Law criteria (aspartate aminotransferase [AST] or alanine aminotransferase [ALT] ≥ 3 × upper limit of normal [ULN] and total bilirubin ≥ 2 × ULN). All study drugs must be permanently discontinued in any patient meeting Hy's Law criteria.

Each patient will be evaluated for toxicity during the Treatment Phase. The toxicity of G1T38 administered with osimertinib will be assessed by the investigators using National Cancer Institute (NCI) CTCAE, Version 4.03.

6.1.2. Part 2

In Part 2, eligible patients will be enrolled into a randomized portion of the study. Patients will be randomized (1:1) to receive osimertinib or G1T38 (at the RP2D) + osimertinib. Following screening, patients will begin once daily oral dosing with osimertinib or G1T38 + osimertinib on Cycle 1 Day 1.

Patients who are initially randomized to receive osimertinib alone may crossover to G1T38 + osimertinib at the time of disease progression as determined by blinded independent central review (BICR). Patients should continue osimertinib monotherapy uninterrupted prior to crossover. The date of crossover is defined as the first date the patient receives G1T38 + osimertinib.

An independent data monitoring committee (IDMC) shall review all cumulative safety and efficacy data, as well as all available PK data, approximately every 4 months during the Treatment Phase of Part 2 of the study. The IDMC shall make recommendations regarding continuation of the study, suggested modification of the study, or cessation of the study based on cumulative safety and efficacy data, including cessation for futility. Further details with respect to decision making will be described in the IDMC Charter.

7. STUDY POPULATION

7.1. Selection of Patients

Overall, up to 144 patients may be enrolled in the study.

In Part 1, up to 36 patients may be enrolled.

In Part 2, up to 108 patients will be enrolled.

7.1.1. Inclusion Criteria

Patient eligibility shall be reviewed and documented by an appropriately qualified member of the investigator's study team before patients are included in the study. Patients must meet all of the following inclusion criteria to be eligible for enrollment into the study:

- 1. Provision of signed and dated written informed consent prior to any study specific procedures, sampling, and analysis
- 2. Women or men, 18 years or older
- 3. Histologic or cytologic confirmed diagnosis of NSCLC
- 4. Stage IV NSCLC
- 5. Documented EGFR mutation (at any time since the initial diagnosis of NSCLC) known to be associated with EGFR TKI sensitivity (including G719X, exon 19 deletion, L858R, L861Q). Patients in Part 1 that are EGFR TKI treatment naive will be enrolled based on a locally available EGFR mutation test result that has been FDA-approved and performed in a Clinical Laboratory Improvement Amendments (CLIA)-certified laboratory (US sites) or based on a locally available EGFR mutation test result that has been performed in an accredited laboratory (sites outside of the US).
 - a. *Part 2 Only*: Tumor EGFR T790M mutation-positive status after documented disease progression on first-line treatment with a first or second generation EGFR TKI. Patients will be enrolled based on a locally available T790M mutation test result (tumor biopsy or cell-free DNA [cfDNA]) that has been FDA-approved (eg, cobas[®] EGFR Mutation Test v2, FoundationOne CDxTM) and performed in a CLIA-certified laboratory (US sites) or a locally available T790M mutation test result (tumor biopsy or cfDNA) that has been performed in an accredited laboratory (sites outside of the US). Testing for the presence of the T790M mutation in plasma specimens (cfDNA) is recommended only in patients for whom a tumor biopsy cannot be obtained.
- 6. Eastern Cooperative Oncology Group (ECOG) performance status of 0 or 1, with no deterioration over the previous 2 weeks and a minimum life expectancy of 12 weeks

- 7. Evaluable disease (Part 1 only) or measurable disease as defined in Response Evaluation Criteria in Solid Tumors (RECIST), Version 1.1, as determined by the investigator
 - Measurable disease is defined as having at least 1 lesion, not previously irradiated, that can be accurately measured at baseline as ≥ 10 mm in the longest diameter (except lymph nodes, which must have short axis ≥ 15 mm) with computerized tomography (CT) or magnetic resonance imaging (MRI), which is suitable for accurate repeated measurements.
- 8. Left ventricular ejection fraction (LVEF) ≥ institution's lower limit of the reference range
- 9. Adequate bone marrow reserve or organ function as demonstrated by the following laboratory values:
 - a. Hemoglobin $\geq 90 \text{ g/L}$
 - b. ANC $\ge 1.5 \times 10^9 / L$
 - c. Platelet count $> 100 \times 10^9/L$
 - d. Calculated creatinine clearance ≥ 50 mL/min (by Cockcroft-Gault formula [Cockcroft and Gault 1976] or ⁵¹Cr-EDTA)
 - e. Total bilirubin $\leq 1.5 \times ULN$; $< 3 \times ULN$ if the patient has documented Gilbert's disease or liver metastases
 - f. ALT $< 2.5 \times$ ULN if no demonstrable liver metastases or $< 5 \times$ ULN in the presence of liver metastases
 - g. AST $< 2.5 \times$ ULN if no demonstrable liver metastases or $< 5 \times$ ULN in the presence of liver metastases
- 10. Contraception: Patients must be willing to comply with the requirements for contraception as described in Section 8.10

Additional criteria that apply to Part 2 only:

11. Measurable disease as defined in RECIST, Version 1.1, as determined by the investigator

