- 8. *Part 1:* Patients receiving medications that raise gastric pH within 7 days prior to first dose of study drug such as proton pump inhibitors (eg, omeprazole, pantoprazole, lansoprazole, esomeprazole, rabeprazole, dexlansoprazole), H2 blockers (eg, nizatidine,

- famotidine, cimetidine, ranitidine), and antacids (eg, sodium bicarbonate, calcium carbonate, aluminum-based antacids, magnesium compounds, alginic acid).
- 9. Any unresolved toxicities from prior surgeries or therapy of > Grade 1 (CTCAE, Version 4.03) at the time of starting study drug with the exception of alopecia (any grade) and platinum therapy-related peripheral neuropathy (> Grade 2)
- 10. Known active uncontrolled or symptomatic central nervous system (CNS) metastases, carcinomatous meningitis, or leptomeningeal disease as indicated by clinical symptoms, cerebral edema, and/or progressive growth. Patients with a history of CNS metastases or cord compression are eligible if they are currently asymptomatic and clinically stable off anticonvulsants and steroids for at least 28 days prior to first dose of G1T38.
- 11. Any evidence of severe or uncontrolled systemic diseases, including uncontrolled hypertension and active bleeding diatheses, which in the investigator's opinion makes it undesirable for the patient to participate in the study or which would jeopardize compliance with the protocol
- 12. Known chronic, active infection including but not limited to hepatitis B virus, hepatitis C virus, tuberculosis, and human immunodeficiency virus (HIV); screening for chronic conditions is not required
- 13. Any of the following cardiac criteria:
 - a. Mean resting corrected QT interval (QTc) > 470 msec obtained from 3 electrocardiograms (ECGs), using the screening clinic ECG machine derived QTc value
 - b. Any clinically important abnormalities in rhythm, conduction, or morphology or resting ECG, eg, complete left bundle branch block, third degree heart block, second degree heart block, PR interval > 250 msec
 - c. Any factors that increase the risk of QTc prolongation (see Appendix 3 for list of drugs) or risk of arrhythmic events such as heart failure, hypokalemia, congenital long QT syndrome, family history of long QT syndrome or unexplained sudden death under 40 years of age in first degree relatives, or any concomitant medication known to prolong the QT interval

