8.3.3.2. Osimertinib

Dose modifications for osimertinib for adverse reactions are to be made according to Table 8-2.

If a patient experiences a Grade 3 (CTCAE) or higher and/or unacceptable toxicity (any grade), where the investigator considers the AE of concern to be specifically associated with osimertinib (and not attributable to the disease or disease-related processes for which the patient is being treated), dosing will be interrupted and supportive therapy administered as required in accordance with local practice/guidelines.

If a toxicity resolves or reverts to \leq Grade 2 (CTCAE) within 3 weeks of onset, treatment with osimertinib may be restarted at the same dose or a lower dose using the rules below for dose modifications (Table 8-2) and with discussion and agreement with the sponsor's study team physician as needed. There will be no individual modifications to dosing schedule in response to toxicity, only potential dose reduction or dose interruption.

If the toxicity does not resolve to \leq Grade 2 (CTCAE) after 3 weeks, then osimertinib therapy shall be permanently discontinued and the patient shall be observed until resolution or stabilization of the toxicity.

Patients experiencing any of the following AEs will not be permitted to restart osimertinib treatment:

- Corneal ulceration
- Interstitial lung disease (ILD)
- QTc interval prolongation with signs/symptoms of serious arrhythmia
- Symptomatic congestive heart failure or asymptomatic left ventricular dysfunction that persists ≥ 4 weeks
- Liver function test abnormalities meeting Hy's Law criteria (AST or ALT \geq 3 × ULN and total bilirubin \geq 2 × ULN). All study drugs must be permanently discontinued in any patient meeting Hy's Law criteria.

Table 8-2 Recommended Dose Modifications for Osimertinib-Related Adverse Reactions

Target Organ	Adverse Reaction ^a	Dose Modification
Pulmonary	Interstitial lung disease/ pneumonitis	Permanently discontinue osimertinib
Cardiac	QTc interval > 500 msec on at least	Withhold osimertinib until QTc interval is
	2 separate ECGs	< 481 msec or recovery to baseline, then resume
		at 40 mg dose
	QTc interval prolongation with	Permanently discontinue osimertinib
	signs/symptoms of life-threatening	
	arrhythmia	
	Symptomatic congestive heart failure	Permanently discontinue osimertinib
	or asymptomatic left ventricular	
	dysfunction that persists ≥ 4 weeks	
Other	≥ Grade 3 adverse reaction	Withhold osimertinib for up to 3 weeks

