10.6.1.1. Definition of Adverse Event

An AE is defined as any untoward medical occurrence in a patient administered a medicinal product that does not necessarily have a causal relationship with this treatment. An AE can, therefore, be any unfavorable and unintended sign (including an abnormal laboratory finding), symptom, or disease temporally associated with the use of a medicinal (investigational) product, whether or not related to the study (investigational) product.

Adverse events include the following:

- All suspected study drug-related adverse events
- All reactions from medication overdose, abuse, withdrawal, sensitivity, or toxicity
- Apparently unrelated illnesses, including the worsening of a pre-existing illness (see pre-existing conditions below)
- Injury or accidents (Note that if a medical condition is known to have caused the injury or accident [eg, a fall secondary to dizziness], the medical condition [dizziness] and the accident [fall] should be reported as 2 separate AEs). The outcome of the accident (eg, hip fracture secondary to the fall) should be recorded under comments.
- Abnormalities in physiological testing or physical examination (findings that require clinical intervention or further investigation beyond ordering a repeat [confirmatory] test)
- Laboratory abnormalities that are clinically significant and require clinical intervention or further investigation (beyond ordering a repeat [confirmatory] test) unless they are associated with an already reported clinical event. Laboratory abnormalities associated with a clinical event (eg, elevated liver enzymes in a patient with jaundice) should be described under comments on the report of the clinical event rather than listed as a separate AE.

An AE does not include:

- Medical or surgical procedures (eg, surgery, endoscopy, tooth extraction, transfusion); the condition that leads to the procedure may be an AE
- Pre-existing diseases or conditions present or detected at the start of the study that do not worsen
- Situations where an untoward medical occurrence has not occurred (eg, hospitalization for elective surgery, social, and/or convenience admissions)
- Overdose of either study drug or concomitant medication without any signs or symptoms
- Progression of the malignancy under study, including signs and symptoms progression

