10.6.1.2. Definition of Serious Adverse Event

The International Council for Harmonisation (ICH) topic E2A on Clinical Safety Data Management, Definitions and Standards for Expedited Reporting defines an SAE as any untoward medical occurrence that at any dose:

- Results in death
- Is life threatening

 NOTE: The term "life threatening" in the definition of "serious" refers to an event in which the patient was at risk of death at the time of the event; it does not refer to an event which hypothetically might have caused death if it were more severe.
- Requires inpatient hospitalization or prolongation of existing hospitalization
- Results in persistent or significant disability/incapacity
- Is a congenital anomaly/birth defect

Medical and scientific judgment should be exercised in deciding whether expedited reporting (see Section 10.6.1.9) is appropriate in other situations, such as important medical events that may not be immediately life threatening or result in death or hospitalization but may jeopardize the patient or may require intervention to prevent one of the other outcomes listed in the definition above. These should also usually be considered serious. Examples of such events are intensive treatment in an emergency room or at home for allergic bronchospasm; blood dyscrasias or convulsions that do not result in hospitalization; or development of drug dependency or drug abuse.

To ensure there is no confusion or misunderstanding of the difference between the terms "serious" and "severe", the following note of clarification is provided:

The term "severe" is often used to describe the intensity (severity) of a specific event (as in mild, moderate, or severe myocardial infarction); the event itself, however, may be of

relatively minor medical significance (such as severe headache). This is not the same as "serious," which is based on patient/event outcome or action criteria usually associated with events that pose a threat to a patient's life or functioning. Seriousness (not severity) serves as a guide for defining regulatory reporting obligations.

Hy's Law

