Prompt reporting (via the SAE expedited reporting system) of cases meeting Hy's law criteria (AST or ALT \geq 3 \times ULN and total bilirubin \geq 2 \times ULN) is required for compliance with regulatory guidelines. The investigator is responsible for, without delay, determining whether a patient meets potential Hy's law criteria. Any patient with liver function test abnormalities meeting Hy's Law criteria must have all study drugs permanently discontinued.

Additional Reporting Requirements for Osimertinib

The following will also be reported to pharmacovigilance: any osimertinib overdose; if a patient taking osimertinib begins lactating; or if a male patient taking osimertinib fathers a child during the treatment period, including the Post-Treatment Follow-up visit. If these events also meet the criteria to be considered an SAE, they shall be reported as such.

Handling of Deaths

All deaths that occur during the study, or within the follow-up period after the administration of the last dose of investigational product, should be reported as described below.

Death, which is unequivocally due to disease progression, should be communicated to the study monitor at the next monitoring visit and should be documented in the eCRF module, but should not be reported as a SAE during the study

Where death is not clearly due to disease progression, the AE causing the death should be reported to the study monitor as an SAE within 24 hours. The report should contain a comment regarding the co-involvement of progression of disease, if appropriate, and should assign a single primary cause of death together with any contributory causes.

Deaths with an unknown cause should always be reported as a SAE but every effort should be made to establish a cause of death. A postmortem may be helpful in the assessment of the cause of death, and if performed, a copy of the post-mortem results (with translation of important parts into English) shall be reported, if possible, to the sponsor.

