11.3. Discontinuation of Study Drug

Study drug(s) shall be discontinued if any of the following events occur during the study:

- A patient suffers an AE that, in the judgment of the investigator, sponsor, or medical monitor, presents an unacceptable risk to the patient (see Section 8.3.3.2 for additional details).
- General or specific changes in the patient's condition (eg, a significant intercurrent illness or complication) that, in the judgment of the investigator, are unacceptable for further administration of study drug
- Occurrence of pregnancy
- Significant noncompliance with protocol requirements
- The sponsor or legal representative of the sponsor requests the patient to withdraw
- Patient has radiographically documented or clinically determined disease progression, with the exception of patients in Part 2 that crossover from osimertinib alone to G1T38 + osimertinib at the time of disease progression.

In the event of study drug discontinuation, patients shall be strongly encouraged to complete all scheduled assessments; the Post-Treatment Visit; and the Survival Follow-up Phase of the study. A patient who discontinues study drug for reasons other than PD shall have a CT or MRI scan at the Post-Treatment Visit, if they have not had a scan within the prior 4 weeks and the patient does not plan to return for subsequent post-treatment scans.

When discontinuation is due to a SAE or a Grade 3 or 4 toxicity considered to be related to study drug, the investigator shall follow the event until resolution, return to baseline, or it is deemed that further recovery is unlikely.

In the event a patient discontinues due to an AE or pregnancy, the investigator shall notify the medical monitor or PPD Safety Services by telephone within 24 hours of study drug discontinuation.

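### For patients with liver metastases, the entry limits admit liver values that already meet the protocol's numeric Hy's Law stopping criterion, and no text states a baseline exception

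*Protocol*

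**What the plan says.** **Entry.** Protocol 7.1.1, inclusion 9e, caps total bilirubin at 1.5 × ULN but relaxes this to below 3 × ULN "if the patient has documented Gilbert's disease or liver metastases". Inclusions 9f and 9g cap ALT and AST below 2.5 × ULN, or below 5 × ULN with liver metastases.

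**Stopping and reporting.** Throughout the protocol, Hy's Law means AST or ALT ≥ 3 × ULN together with total bilirubin ≥ 2 × ULN. Section 10.6.1.2 states: "Any patient with liver function test abnormalities meeting Hy's Law criteria must have all study drugs permanently discontinued". It also requires "Prompt reporting (via the SAE expedited reporting system) of cases meeting Hy's law criteria".

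**Where else the rule appears.** It is in the DLT definition (Synopsis and 6.1.1.2), under G1T38-related nonhematologic toxicity (8.3.3.1), in the osimertinib no-restart list (8.3.3.2), and in a paragraph on permanent discontinuation for toxicity (8.3.3.2.4).

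**SAP.** Section 7 redefines Hy's Law for analysis, adding ALP < 2 × ULN. Section 5.2.10 plans a separate listing of patients who met it. The same section calls a graded laboratory abnormality treatment-emergent only if it is at least one grade above baseline. The text on the Hy's Law listing has no such condition.

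**The concern.** Two stated rules collide. One declares a patient eligible; the other, taken at its word, takes the same patient off all study drugs for good on the same values. Clinical chemistry is scheduled on Cycle 1 Day -16 and again on Cycle 1 Day 1 (Table 9-1), so the question could arise almost at once.

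Two sites could each believe they were compliant and act in opposite ways, one withdrawing the patient and the other continuing. Under 6.1.1, a Part 1 patient withdrawn during the DLT period for a reason other than toxicity is replaced, so a literal stop could also cost an extra patient. In the report, the Hy's Law listing could show a case that reflects liver metastases rather than drug, with nothing in the SAP text to mark it.

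**Working it through.** The plan gives no figure on this point, so there is none to reproduce. The check compares thresholds and then the texts.

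**Step 1. Intersect entry limits with the criterion** (multiples of ULN; entry limits from Protocol 7.1.1, criterion from 10.6.1.2).

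| Group | ALT, AST allowed | Bilirubin allowed | Criterion met at entry? |
|---|---|---|---|
| Liver metastases | < 5 | < 3 | Possible: ALT or AST from 3 to < 5, with bilirubin from 2 to < 3 |
| Gilbert's disease, no liver metastases | < 2.5 | < 3 | No: the ≥ 3 transaminase limb is out of reach |
| Neither | < 2.5 | ≤ 1.5 | No: both limbs are out of reach |

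Example with liver metastases: for ALT 4, AST 4 and bilirubin 2.5, entry requires 4 < 5, 4 < 5 and 2.5 < 3, all true. The criterion requires 4 ≥ 3 and 2.5 ≥ 2, both true. A grid in steps of 0.1 × ULN gave the same region and no overlapping point in the other two groups.

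**Step 2. Look for a baseline exception.** None of the Hy's Law texts listed above requires a rise from baseline or sets a different threshold for liver metastases. Exclusion 9 (7.1.2) does not close the gap. It covers "Any unresolved toxicities from prior surgeries or therapy of > Grade 1", not abnormalities caused by the metastases themselves.

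**Step 3. Repeat with the SAP definition.** SAP Section 7 prints the transaminase limb with a stray extra factor of 3; I read it as > 3 × ULN. The overlap is then ALT or AST above 3 and below 5, bilirubin from 2 to below 3, and ALP below 2. Inclusion 9 sets no ALP limit. The ALP condition removes some cases but is not a comparison with baseline.

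**Step 4. Size.** The documents give no share p of patients with liver metastases and both abnormalities. For illustration only, assume p from 0.5% to 3% of those enrolled; nothing in the documents supports this range. With n = 36, the Part 1 maximum:

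- Expected number = 36p: 36 × 0.005 = 0.18, to 36 × 0.03 = 1.08.
- Chance of at least one = 1 − (1 − p)^36: 1 − 0.995^36 = 16.5%, to 1 − 0.97^36 = 66.6%.
- Chance of 0 or 1 = (1 − p)^36 + 36p(1 − p)^35: 0.835 + 0.151 = 99%, down to 0.334 + 0.372 = 71%.
- For the six patients of Cohort 1 alone, the chance of at least one is 1 − (1 − p)^6, or 3.0% to 16.7%.

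Actual enrolment may be below 36 (SAP 2.3), which lowers these figures. The SAP states that Part 2 will not be conducted.

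**The case against.** The strongest reply is that the rule was meant for adverse events, and much of the text supports this:

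- The DLT sections cover drug-related AEs only, and 8.3.3.1 and 8.3.3.2.4 place the rule under toxicity headings.
- Section 8.3.3.2 introduces its list with "Patients experiencing any of the following AEs will not be permitted to restart osimertinib treatment".
- Section 10.6.1.2 itself "defines an SAE as any untoward medical occurrence that at any dose" meets one of the listed outcomes.
- Section 10.6.1.1 says an AE does not include "Pre-existing diseases or conditions present or detected at the start of the study that do not worsen".
- Section 9.1 sends events before first dose to medical history, and 10.6.1.9 starts SAE reporting at first dose.
- Among the discontinuation triggers in 11.3 is "A patient suffers an AE that, in the judgment of the investigator, sponsor, or medical monitor, presents an unacceptable risk to the patient".

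This stands as the better reading everywhere except 10.6.1.2. It does not remove the conflict there, where the stop applies to any patient meeting the numbers and none of these texts qualifies it. A permanent stopping rule should not depend on a site assembling its exception from several general definitions.

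Two further replies stand in part. Exclusion 11, which rests on the investigator's opinion about severe or uncontrolled systemic disease, may keep some such patients out, but need not. And a stop at these values whatever the cause is a defensible conservative rule; if that is the intent, such patients should not be enrolled.

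A reader might infer more than the documents support. Stable baseline disease would not count as a DLT, because DLTs must be drug-related AEs, so no bias in the RP2D follows. The quoted bilirubin clause names Gilbert's disease, but Gilbert's disease alone creates no overlap. Nor is an inflated Hy's Law count shown: the SAP specifies a listing, does not say whether its tabulation of hepatic abnormalities includes Hy's Law, and leaves layouts to shells that are not in these documents.

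**Conclusion.** The point holds as a minor inconsistency limited to patients with liver metastases. The overlap is certain from the stated limits. What remains open is how a site would act, because the literal stop rests on 10.6.1.2 while the surrounding text leans towards an AE-based reading.

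The frequency cannot be derived from the documents. The expectation of 0 or 1 patient in Part 1 rests on the assumed range above. The effect is confined to the handling of an individual patient and the interpretation of a listing. Part 1 is descriptive with no formal test, and general laboratory listings would let a reader check baseline values by hand. The SAP part also assumes that the unseen listing shells do not already carry a baseline marker.

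**What to change.** **Protocol.** Add to inclusion 9 that AST or ALT ≥ 3 × ULN and total bilirubin ≥ 2 × ULN must not both be present on the last sample before first dose. This empties the overlap under both the protocol and SAP definitions. Patients with liver metastases and only one abnormality stay eligible. The cost is one sentence and the exclusion of a very few patients. A patient who enters just below a threshold and then crosses it would still be stopped, but that is a change after entry and a different matter. If Part 1 enrolment has closed, which the documents do not state, this change is moot.

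**SAP.** In the Hy's Law listing of Section 5.2.10, flag each patient whose thresholds under the Section 7 definition, including ALP < 2 × ULN, were already met at the safety baseline of Section 4. The four analytes are in SAP Table 8 and the baseline is already defined, so the cost is one derived flag. No separate treatment-emergent count is needed, because no Hy's Law table is specified. The stray factor in the Section 7 definition should be corrected at the same time.
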